#### **D. RESEARCH DESIGN AND METHODS AND DATA ANALYSIS**

**Research Design.** We will invite 56 women with an APO within the past 3 yrs to participate. Women will be randomly assigned to the 4-wk intervention group (n=28) or a standard care group (n=28) using a computerized random number generator, stratified by race. Assuming up to 25% with poor adherence, we expect that 42 women (21 each arm) will complete the study. No data exists related to effects of supplementation on vascular function in our population, we assumed a medium effect size, i.e. Cohen's  $d \sim 0.50$  and accepting a  $\beta=0.80$ , to generate sample sizes. Generation of effect sizes is a key outcome of this study. We will conduct a vascular assessment and blood draw at two visits: before the intervention begins and within 3 days of completing the intervention. We will conduct visits during the early follicular phase of menstrual cycle to account for fluctuating hormones. Vascular testing will be performed in the supine position and  $\geq 4$  hours after a light meal. Surveys for Aim 2 will be completed within the first 2 weeks of study enrollment, and interviews for Aim 2 will be conducted within 1 week of Visit 2, in-person or via telephone.

**Anti-inflammatory supplementation intervention.** Participants randomized to the supplementation intervention will receive PolyResveratrol-SR® (100 mg curcumin phytosome, 100 mg quercetin phytosome, 100 mg green tea phytosome, 100 mg trans-resveratrol, 100 mg trans-pterostilbene; Thorne Research). Participants will be asked to take 2 doses/day (1g total). Participants randomized to supplementation will receive a daily email reminding them to take the supplement. **Covariates.** Medical history, age, and sociodemographics will be obtained via self-report. We will use validated surveys to determine physical activity, sedentary behavior, and smoking history. Height and weight will be measured.

**Aim 1 Outcomes.** The outcomes will be measured in-person. All outcomes are listed and described below. [name] has extensive experience collecting the measurements described below.

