1. **Blood pressure.** Resting brachial systolic BP (SBP) and diastolic BP (DBP) will be measured using an automated oscillometric cuff (HEM-907 XL; Omron, Shimane, Japan) after 10 min of supine rest in a quiet, dimly lit room. Brachial BP will be obtained in duplicate with 1 min between the first and second reading. If the two values are not within 5 mmHg of each other, another measurement was taken until two consecutive values within 5 mmHg of each other are obtained. These two values will be averaged and used for analysis.
2. **Arterial stiffness.** Participants will remain supine in a quiet room. The aortic waveform will be reconstructed from radial artery pressure waveforms obtained from a 10-s epoch

using applanation tonometry (Millar Instruments, Houston, TX) and calibrated with brachial MAP and diastolic BP with a generalized validated transfer function (SphygmoCor; AtCor Medical, Sydney, Australia). From this central waveform, we will derive central BP, augmentation index (AIx), and end-systolic pressure. An in-device quality rating of  $\geq 80\%$  will be required for all recordings used in analysis. We will measure central (aortic) pulse wave velocities in the supine position using gold-standard techniques. We will measure distances from the suprasternal notch to the femoral artery and from the carotid artery to the suprasternal notch with a tape measure, recorded to the nearest mm. The distance from the carotid site to the suprasternal notch will be subtracted from the distance between the suprasternal notch and femoral artery to account for the divergent directions of pulse wave propagation. We will use the same high-fidelity strain-gauge transducer to obtain pressure waveforms at the right common carotid artery and then at the right femoral artery for central pulse wave velocity. Pulse wave velocity will be calculated as distance/time, using the distances between measurement points and the measured time delay between 10 proximal and distal waveforms (SphygmaCor; AtCor Medical). ECG will be recorded simultaneously, and the peak of the R wave will be our timing marker. BP influences pulse wave velocity, so we will also adjust pulse wave velocity for aortic MAP.

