3. *Resting forearm blood flow*. Forearm blood flow (FBF) will be measured using strain gauge plethysmography (EC-4; Hokanson, Inc., Bellevue, WA). A standard BP cuff will be positioned around the upper arm. An appropriately sized strain gauge will be placed around the widest part of the forearm, and a pediatric cuff placed around the wrist to occlude hand blood flow. Before measuring FBF, the wrist cuff will be inflated to 250 mm Hg of pressure for 1 minute. FBF will be determined by inflating the upper cuff to 50 mm Hg (to oppose venous backflow) for 7 s and then deflating it for 8 s. An average of six of these 15-s plethysmographic cycles will be used to determine FBF, expressed as milliliters per minute per 100 mL of forearm tissue and as flow per unit pressure, e.g. conductance, using the equation:  $conductance = (FBF/MAP) \times 1000$ .
4. *Vascular endothelial function*. Reactive hyperemia, e.g. resistance vessel endothelial function, will be measured immediately after FBF. Arm blood flow will be occluded by inflating the upper arm BP cuff to 250 mm Hg for 5 min. One minute prior to the release of the upper arm cuff, the wrist cuff will also be inflated to 250 mm Hg. The upper arm cuff pressure will be rapidly released and changes in forearm volume will be recorded via the strain gauge, in 15-s cycles as described above, for 3 min (13 readings). The highest reading will represent peak blood flow. All 13 measurements will be plotted against time, and the area under this curve will represent total reactive hyperemia. We chose to measure reactive hyperemia rather than flow-mediated dilation due to the high intra- and interobserver variability in flow-mediated dilation measurements.
5. *Carotid intima-media thickness*. The right common carotid artery will be imaged with ultrasound (Logiq GE S8) using a 12-MHz linear array probe. Intima-medial thickness will be defined as the distance between the leading edge of the lumen–intima border and the leading edge of the media–adventitia border on the far wall of the artery. We will average a 5mm segment obtained approximately 20 mm proximal to the carotid bifurcation for analysis.

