#### **Aim 2 Outcomes:**

1. **Acceptability of Dietary Supplementation.** We will administer surveys to all participants to understand their perceptions of dietary supplementation, including potential benefits and consequences associated with supplementation. We will determine willingness to use supplements, barriers to supplementation, and who, i.e., physician or partner, influences their decision to use dietary supplements.
2. **Adherence and Barriers to Adherence.** We will count pills to determine adherence to supplementation regime. We will assess each intervention participant’s perceptions of supplementation with a brief interview at the final visit. Interviews will capture participant’s perceptions of the role of supplementation for CVD prevention, and any side effects of supplementation. We will ask participants to recommend ways to encourage participation and ask questions regarding their perceptions of the incentive structure and contact with the study team. We will contact participants who drop out of the study to identify reasons for drop out.

**Statistical analyses:** Acceptability survey data will be collected using a Likert Scale, tallied and averaged. We will determine the proportion of participants with adequate adherence ( $\geq 80\%$ ) to supplementation. If  $\geq 80\%$  of women have adequate adherence, we will conclude acceptable adherence is feasible with the existing incentive structure. Analysis of all post-intervention interview data will use an inductive approach and systematically guided by the constant

comparison technique. Qualitative data analysis software (QRS NVivo 10) will be used to code data and organize the analysis.

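### The plan states no masking of operators, readers or laboratory staff in a trial with a standard-care control, and does not place the pill count and interview after Visit 2 testing

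*Combined protocol and SAP*

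**What the plan says.** The Research Design paragraph of Section D assigns women to four weeks of supplement "or a standard care group (n=28) using a computerized random number generator, stratified by race". No placebo is described. Contact also differs by arm: "Participants randomized to supplementation will receive a daily email reminding them to take the supplement".

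On how Aim 1 outcomes are obtained, Section D says "The outcomes will be measured in-person" and that one named person "has extensive experience collecting the measurements described below". It does not say how many people acquire or read the recordings, or whether any of them is kept unaware of allocation. The Aim 1 items then describe:

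- hand-held tonometry, with path lengths for pulse wave velocity taken "with a tape measure, recorded to the nearest mm" (item 2);
- strain-gauge plethysmography at rest and after occlusion (items 3 and 4);
- carotid ultrasound: "We will average a 5mm segment obtained approximately 20 mm proximal to the carotid bifurcation for analysis" (item 5).

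Under Aim 2 Outcomes, item 2, "We will count pills to determine adherence to supplementation regime"; no time or person is given. The same item places the interview with supplement-arm women at the last visit. The Research Design paragraph instead allows it up to a week from Visit 2, face to face or by telephone.

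De-identification appears under Blood analyses (Section D, item 6), for storage and future analyses, and under Confidentiality (Section E, item 7). Neither describes it as masking to arm.

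**The concern.** Every woman knows her arm, and nothing in the plan keeps that knowledge from the person holding the probe, tonometer or tape, or from whoever later reads the files. The interview is held only with supplement-arm women, and only they have pills to count. If either came before the vascular tests at Visit 2, it would disclose allocation to anyone present. Visit 1 is set before the intervention starts, but the plan does not say that it precedes disclosure of the allocation, so the baseline readings are not clearly protected either.

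Section D names generation of effect sizes as a key outcome. A systematic reading difference between arms is added directly to the estimated effect. It cannot be separated from a supplement effect in the analysis, and a larger sample does not remove it.

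**Working it through.** **1. Is masking stated anywhere?** The sections on design, intervention, Aim 1 outcomes, data analysis, Aim 2 and human subjects contain no provision for operators, readers or laboratory staff. The plan gives no figure for observer bias, so there is none to reproduce.

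**2. How exposed is each outcome?**

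| Outcome | Step that depends on the operator | Safeguard in the plan |
|---|---|---|
| Pulse wave velocity, central waveform | Tonometer handling; tape-measured distance | Device quality rating of at least 80% for recordings; none for the tape |
| Plethysmography | Gauge and cuff placement; reading method not stated | Fixed rules: mean of six cycles, highest reading, area under 13 readings |
| Carotid intima-media thickness | Probe position and segment | Site, segment length and borders defined; reader and software not stated |
| Brachial BP | Little | Automated cuff, fixed repeat rule |
| Biomarkers | Little | Commercial ELISA kits |

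The first three rows carry the point.

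**3. When could the arm be revealed at Visit 2?** The pill count is untimed. The interview is at the last visit in one passage and within a week of Visit 2 in the other. Neither passage requires testing to come first. Disclosure before testing is therefore permitted, though not prescribed.

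**4. What would a given bias do? (illustration)**

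Inputs from Section D: 28 per arm randomised; 25% expected loss, so 28 × 0.75 = 21 per arm completing; planned effect d = 0.50.

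Assumptions: the bias b in SD units; no true effect; a two-sample t test at two-sided 5%. The plan states neither alpha nor a between-arm test.

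The rejection rate is the probability that |T| exceeds the 97.5% point of t with 2n − 2 degrees of freedom, where T is noncentral t with noncentrality b × √(n/2).

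- n = 21: √10.5 = 3.24, df = 40.
- n = 28: √14 = 3.74, df = 54.

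| Assumed b | b / 0.50 | Noncentrality, n = 21 / 28 | False-positive rate, n = 21 / 28 |
|---|---|---|---|
| 0.1 SD | 20% | 0.32 / 0.37 | 6.2% / 6.6% |
| 0.2 SD | 40% | 0.65 / 0.75 | 9.7% / 11.4% |
| 0.3 SD | 60% | 0.97 / 1.12 | 15.8% / 19.7% |

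The second column matters more for a pilot: it is the error carried into the effect size, as a share of the effect planned for, and it does not depend on n.

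**The case against.** The strongest reply is that the measurements are more tightly specified than this point might suggest. That is largely true. BP comes from an automated cuff, and the repeat rule ("another measurement was taken until two consecutive values within 5 mmHg of each other are obtained") limits discretion rather than showing it. Tonometry has a device quality threshold, plethysmography has fixed summary rules, and the carotid site and borders are defined. The investigators also considered observer variability, since they preferred reactive hyperemia to flow-mediated dilation on that ground. What stands after this is the tape measure, the handling of probe, tonometer and gauge, and an unstated reading process. Fixed rules reduce random scatter, but they do not keep the arm from the person applying them.

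Three stronger readings are tempting and are not supported.

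- A reader might infer that the pill count and interview both take place at the final visit. The pill count has no stated time, and the design paragraph allows the interview on another day and by telephone. The supportable finding is a conflict and an unspecified order.
- A reader might infer that masked reading needs no additional person. The documents give no staffing and do not say who reads the files. Someone who acquired the images may recognise them even under a code.
- A reader might take the higher false-positive rates as what to expect. The bias is assumed, exposure differs by outcome, and at 0.1 SD the inflation is small.

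**Conclusion.** The point holds as an omission that can be improved cheaply. In a trial without placebo, several operator-dependent outcomes are measured and read with no stated masking, and the plan permits events that reveal the arm to precede Visit 2 testing. This leaves the effect-size estimates open to observer bias. It does not show that bias will occur.

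The size cannot be derived from the documents. Under the assumptions above, the false-positive rate runs from about 6% (0.1 SD, at 21 or 28 per arm) to 19.7% (0.3 SD, 28 per arm). At the 21 completers per arm that the plan expects, the upper figure is 15.8%. The concern applies to pulse wave velocity and other tonometry measures, plethysmography and carotid thickness; it applies much less to automated BP and the ELISA biomarkers.

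**What to change.** 1. State in Section D who is and is not masked: operator, reader and laboratory staff.
2. Complete Visit 1 testing before the allocation is revealed to the participant or the operator.
3. At Visit 2, do the vascular tests and blood draw before any pill count or interview, and ask women not to mention their arm. Say who counts the pills and when.
4. Reconcile the interview timing in the Research Design paragraph with that in Aim 2 Outcomes, item 2.
5. Store tonometry, plethysmography and carotid files, and blood samples, under codes that show neither arm nor visit. Read or assay them in batch before the code is opened. Where possible, existing staff not involved in pill counts should hold the code.

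Placing a woman's two samples on one ELISA plate is also sensible. It controls assay batch variation and is not masking; the code holder can arrange it.

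Cost: changes to visit order and labelling, and a short delay while reading is batched. No new visit or participant procedure is needed. Whether a further reader is needed depends on staffing that the plan does not describe. Protection is partial: live acquisition rests on visit order and participants' discretion, and a reader who also acquired the images may not be fully masked. The report should state that limit.

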## **A. SPECIFIC AIMS**

- 1. Aim 1. Determine the effects of a 4-week course of anti-inflammatory supplementation (PolyResveratrol-SR®) on vascular function, subclinical atherosclerosis and CV biomarkers**
- 2. Aim 2. Define adherence and barriers to compliance to supplementation.**

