**Data Analyses.** We will calculate the 25th and 75th percentile for each biomarker and vascular function test and use these values as cut-offs for “low” and “high” levels, respectively. We will test for differences in biomarker levels between women by APO status and race using a t-test or Mann-Whitney U test, depending on the distribution of the variables. We will use separate multiple linear regression models to determine associations of each exposure (continuous levels of biomarkers; quartiles; and high or low levels of these biomarkers) with continuous measures of our outcomes (individual indices of vascular function, e.g. BP, arterial stiffness, augmentation index, FBF, endothelial function, and intima-media thickness) in all 56 women. We will use logistic regression to test for associations between continuous and categorical levels of biomarkers with categorical outcomes: the likelihood of having hypertension or prehypertension, high central arterial stiffness, low endothelial function, and high carotid intima-media thickness in all 56 women. We will test for unadjusted associations and then adjust all regression analyses for key co-variables: maternal age, race, and smoking. We will test for associations after furthering adjusting for years of education, body mass index (BMI), parity, and physical activity, in the index pregnancy in exploratory analyses. We will test for an interactive effect of APO status and race on these associations using a multiplicative interaction term in separate analyses and conduct all analyses stratified by APO status and/or race if the interaction is significant. We will conduct a sensitivity analysis by repeating our statistical tests only in the primiparous women as prior pregnancy is associated with lasting changes in vascular function and may influence our outcome and exposure variables.

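### Aim 1 has 15 co-equal outcomes, with no primary, no alpha, no multiplicity rule and no planned comparison between arms, so no single result answers it

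*Combined protocol and SAP*

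**What the plan says.** Section A states Aim 1 as determining the effects of four weeks of supplementation "on vascular function, subclinical atherosclerosis and CV biomarkers". That is three domains, with no order among them.

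Section D, under Aim 1 Outcomes, says "All outcomes are listed and described below". The numbered items then describe:

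- Blood pressure: "Resting brachial systolic BP (SBP) and diastolic BP (DBP) will be measured".
- Arterial stiffness: "we will derive central BP, augmentation index (AIx), and end-systolic pressure". Central pulse wave velocity is also measured, and the plan adds "so we will also adjust pulse wave velocity for aortic MAP".
- Resting forearm blood flow, "expressed as milliliters per minute per 100 mL of forearm tissue and as flow per unit pressure, e.g. conductance".
- Reactive hyperemia, as peak flow and as area under the curve. On the choice of technique the plan says "We chose to measure reactive hyperemia rather than flow-mediated dilation".
- Carotid intima-media thickness.
- IL-6, IL-10, ICAM-1 and VCAM-1.

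The Research Design paragraph gives one generic medium effect size, d about 0.50, for vascular function as a whole. It also says that generating effect sizes is a key outcome. The Data Analyses paragraph plans group comparisons by APO status and race, and regressions of vascular indices on biomarkers in all 56 women. On those it says "We will test for unadjusted associations and then adjust all regression analyses for key co-variables". It does not mention treatment arm.

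**The concern.** A trial that sets out to determine effects, and bases its sample size on one effect size, needs to say which measure that effect size describes and which contrast answers the question. Here the reader can find neither. After the data are in, any of the 15 measures could be presented as the intended one, and the plan offers nothing against which to check that choice.

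Two things are at stake. If the outcomes are tested, the error rate of a statement such as the supplement affected vascular function is not held at 5%. If they are only estimated, the most striking of 15 imprecise estimates is the one most likely to be carried into the design of a later trial.

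**Working it through.** **Count of outcomes (Section D, Aim 1 Outcomes).** Brachial SBP and DBP (2); central BP, augmentation index and end-systolic pressure (3); pulse wave velocity, counted once although a pressure-adjusted version is also planned (1); forearm blood flow and conductance (2); peak and total reactive hyperemia (2); carotid intima-media thickness (1); four biomarkers (4). 2 + 3 + 1 + 2 + 2 + 1 + 4 = 15.

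**The plan's own figure.** The allowance for loss reproduces: 21 / (1 − 0.25) = 28 per arm. The 21 does not follow from d = 0.50 in an ordinary two-arm comparison. Reading the stated β of 0.80 as power, and assuming two-sided 0.05, n per arm = 2(1.96 + 0.84)² / 0.50² ≈ 63 (64 by t-test). That is a separate issue. It matters here only because it gives no clue to which outcome or contrast was intended.

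**Can a primary be inferred?** The documents point three ways. The Background rests on inflammation and names IL-6. The Preliminary Studies highlight central systolic BP. The outcome list gives a reason for measuring reactive hyperemia, but only against flow-mediated dilation as a technique, and it yields two readouts. No passage ranks these.

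**Chance of at least one false positive.** Assumptions, since the plan states none of them: all 15 outcomes compared between arms, each at two-sided 0.05, no true effect on any.

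- Independent: 1 − 0.95¹⁵ = 0.537.
- Equally correlated normal test statistics, by simulation:

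| Pairwise correlation | Chance of ≥ 1 false positive |
|---|---|
| 0 | 54% |
| 0.3 | 46% |
| 0.5 | 36% |
| 0.7 | 26% |
| 0.8 | 20% |

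- Blocks by domain (correlation 0.6–0.8 within, 0.1–0.3 between): 33% to 43%.

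**Selection of the largest estimate.** With 21 completers per arm and no true effect, the standard error of d is about √(2/21) = 0.309. The largest of 15 absolute estimates averages E(max|z|) × 0.309, with E(max|z|) from simulation:

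| Pairwise correlation | E(max\|z\|) | Average largest \|d\| |
|---|---|---|
| 0 | 2.05 | 0.63 |
| 0.3 | 1.96 | 0.61 |
| 0.5 | 1.83 | 0.57 |
| 0.7 | 1.64 | 0.51 |
| 0.8 | 1.50 | 0.46 |

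So noise alone would typically produce a best-looking outcome close to, or above, the assumed 0.50. For comparison, the 95% half-width around a single d of 0.50 with 21 per arm is 1.96 × √(2/21 + 0.25/84) ≈ 0.61.

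**The biomarker–vascular regressions, counted separately.** Linear: 4 biomarkers × 3 codings × 6 indices = 72. Logistic: 4 × 3 × 4 binary outcomes = 48. That is 120 per adjustment level: 240 for the unadjusted and first adjusted levels, and 360 with the third level, which the plan already calls exploratory. None of these tests involves treatment arm.

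**The case against.** The strongest reply is that this is a pilot whose stated purpose includes generating effect sizes, and that no passage announces a success claim on whichever outcome is significant. The error rates above belong to 15 between-arm tests that the plan does not contain, at an alpha that it does not state. All of that is correct, so the figures are conditional. It softens the error-rate point. It does not touch the selection point, which applies to estimation as well. Nor does it supply the missing contrast: followed as written, the plan produces no estimate of a supplement effect at all.

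Three stronger readings are tempting, and the documents do not support them.

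- A reader might infer that a false positive is likely, meaning more probable than not. That needs independence, which the measures rule out. Conductance is forearm flow divided by pressure, peak and total hyperemia come from the same readings, and the central pressure measures come from one waveform calibrated with brachial pressure.
- A reader might add the 240 or 360 regressions to the evidence. They relate biomarkers to vascular indices, so a chance finding among them is not a false claim about the supplement.
- A reader might take the remark on flow-mediated dilation as making total reactive hyperemia the intended primary. It justifies one technique over another and ranks nothing above the other 14 outcomes.

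It is also fair to say that naming a primary will not by itself make the trial conclusive, because power is low.

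**Conclusion.** The point holds. Fifteen co-equal outcomes, no primary, no alpha, no multiplicity rule, an effect size attached to no measure and no between-arm analysis together mean that the plan cannot give one interpretable answer to Aim 1. The first four features and the missing arm comparison are read directly from the text and need no assumption.

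The size does rest on assumptions: with every outcome tested between arms at two-sided 0.05, the family-wise risk is about 4 to 11 times the nominal 5% (20/5 = 4; 54/5 ≈ 11), and the upper end requires independence. Given the pilot purpose, this should be corrected before analysis, but it does not undermine the conduct of the study.

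**What to change.** Before any outcome is analysed by arm, the sponsor should:

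1. Name one primary Aim 1 outcome. Total reactive hyperemia is one candidate; central systolic BP and IL-6 are equally supported by the text. The choice is the sponsor's.
2. Make the between-arm difference in that outcome at Visit 2, adjusted for its Visit 1 value, the single Aim 1 test, with alpha and sidedness stated.
3. Report the other outcomes as between-arm effect sizes with 95% confidence intervals and no claim of significance. This serves the stated aim of generating effect sizes.
4. Separately, label the biomarker–vascular associations exploratory, and use the continuous biomarker in one pre-specified adjusted model (4 biomarkers × 6 indices = 24 linear models).

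The cost is protocol wording: no new participants, visits or assays. The sponsor gives up claiming an effect on whichever outcome turns out significant.

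The change does not cure low power. At d = 0.50 and two-sided 0.05, an unadjusted t-test has about 35% power with 21 per arm and 45% with 28. Baseline adjustment helps by an amount that depends on a Visit 1–Visit 2 correlation that the plan does not give: by normal approximation, power at 21 per arm is about 46% at a correlation of 0.5 and reaches 80% only near 0.82. That should be addressed as its own issue.

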## **B. BACKGROUND AND SIGNIFICANCE**

Adverse pregnancy outcomes (APOs) occur in up to 20% of all pregnancies and are associated with a lifetime of higher cardiovascular disease (CVD) risk. **Aberrant and persistent systemic inflammation is a hallmark of both APOs and CVD.** An inappropriate uterine innate immune response to invading fetal cytotrophoblasts is thought to underlie poor placentation and vascular-related APOs; inflammation of the uterine cavity evokes contractions and contributes to preterm birth. Levels of cytokines involved in endothelial inflammation, an instigating event in hypertensive and atherosclerotic processes, were higher in the 2nd trimester in women destined to have APOs. Women with a past APO have higher levels of systemic inflammation, including c-reactive protein and interleukin-6 (IL-6), in the years after delivery versus women with no APOs. A similar pro-inflammatory cytokine profile has been observed in patients with overt CVD. **Intervening on systemic inflammation may be a viable strategy to interrupt the progression from APO to CVD.**

Dietary supplements, such as polyphenols, are anti-inflammatory and inhibit vascular inflammation with potentially few barriers to adherence. **Given the hypothesized contribution of a persistent pro-inflammatory state to the excess CVD risk observed in women after APO, utilization of a polyphenol dietary supplement to specifically target inflammation holds promise as a low-burden intervention to prevent or delay APO-related CVD.** To our knowledge, efficacy and tolerability of a dietary polyphenol supplement has not been investigated in women with a history of APO. To fill in this critical gap in knowledge, we propose to test the vascular function and CV biomarker, i.e., IL-6, IL-10, intracellular and vascular cell adhesion molecule-1 (ICAM-1 and VCAM-1), responses to a 4-week anti-inflammatory dietary supplementation in a clinical trial pilot study of 56 women, 28 assigned to the intervention and 28 to the control group, in the first 3 years after an APO.

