## **E. PROTECTION OF HUMAN SUBJECTS**

### **1. TARGET POPULATION:**

**Participants and incentives.** We will invite women who had a vascular APO 6 months-3 years ago and were 18 years or older at the time of the APO, to participate. Exclusion criteria: currently pregnant or breastfeeding, current smoking, active cancer, regular use of NSAIDs, steroid medications, statins, or other anti-inflammatory supplements, HIV/AIDS, uncontrolled high blood pressure, unwilling or unable to use a dietary supplement, known sensitivity to resveratrol, curcumin, green tea, or quercetin. We will provide a cash incentive of \$50 after study Visit 1 and Visit 2. If enrollment numbers are below target at 6-months, we will open enrollment to women with a history of gestational diabetes (GDM) as GDM is also associated with inflammation and excess CVD risk in women. We chose the time interval of 6 months to 3 years after delivery because it takes about 6 months to return a pre-pregnancy physiological state, but vascular dysfunction has been documented for at least 3 years after an APO.

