### **3. EXISTING DATA/SAMPLES:**

Not applicable

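### The Aim 1 analysis groups women by APO status, which does not vary under the base eligibility criteria, and never compares the randomised arms

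*Combined protocol and SAP*

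**What the plan says.** Section A gives Aim 1 as the effect of a 4-week supplement course on vascular function, subclinical atherosclerosis and cardiovascular biomarkers. The Research Design paragraph of section D randomises women 28:28 to supplement or standard care, stratified by race. Outcomes are measured before and after the intervention, and generating effect sizes is called a key outcome.

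The population is described three times, each time as women with an APO:

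- Section B: "28 assigned to the intervention and 28 to the control group, in the first 3 years after an APO".
- Section D, Research Design: "We will invite 56 women with an APO within the past 3 yrs to participate".
- Section E.1: "We will invite women who had a vascular APO 6 months-3 years ago".

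Section E.3, on existing data or samples, reads "Not applicable". Section E.1 allows women with a history of GDM to be enrolled if recruitment is below target at 6 months.

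The Data Analyses paragraph then plans:

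- a t-test or Mann-Whitney test: "We will test for differences in biomarker levels between women by APO status and race";
- linear and logistic regressions of vascular outcomes on biomarker levels in all 56 women;
- an interaction: "We will test for an interactive effect of APO status and race on these associations using a multiplicative interaction term";
- a conditional step: "conduct all analyses stratified by APO status and/or race if the interaction is significant".

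**The concern.** There are two linked faults. First, the plan groups women by a variable that takes one value for every woman eligible under the base criteria, so the APO-status test, interaction and stratification cannot give a result. Second, the analyses that can be run are biomarker-outcome associations and race contrasts. None of them estimates the effect of supplementation.

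The second fault matters more. A trial that randomises and measures outcomes at two visits would, if the plan were followed exactly, leave Aim 1 unanswered. Unless the plan is amended first, the choice of contrast, visit, baseline handling and model would be made with the data in hand, across four biomarkers and many vascular indices.

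**Working it through.** **1. Is there an APO-negative group?** Sections B, D and E.1 all require an APO, and E.3 brings in no outside data. The only APO-negative women in the document are the 36 in the section C table, who belong to a separate ongoing study. The planned APO-negative number is therefore 0.

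**2. What can be estimated?** The interaction is on the biomarker-outcome associations, so take the columns: intercept, biomarker, APO, race, APO x race, biomarker x APO, biomarker x race, biomarker x APO x race. Assume two race levels, 16 of 56 (close to the 28% in the APO-positive column of the section C table). The rank result does not depend on that split so long as each race group has at least 2 women with different biomarker values.

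- With APO = 1 for all 56 women, each APO column duplicates another (APO equals the intercept, APO x race equals race, and so on). Rank is 4 of 8.
- With the four APO columns dropped, intercept, biomarker, race and biomarker x race have rank 4 of 4.

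The race comparison, the biomarker x race term and the biomarker regressions can therefore be fitted. The APO terms cannot.

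**3. Does the GDM contingency help?** The document does not say whether a woman with GDM only counts as APO-positive. If she does, nothing changes. If she is coded as a second group, each APO-by-race cell needs 2 women to support an intercept and a slope:

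rank = sum over the four cells of min(2, cell size)

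| Assumed GDM-only women (of 56) | Split by race | Rank (of 8) |
|---|---|---|
| 5 | 2 / 3 | 8 |
| 5 | 1 / 4 | 7 |
| 14 | 1 / 13 | 7 |
| any, one cell empty, other cells at least 2 | – | 6 |

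The terms can be fitted only if recruitment is slow and the women happen to fall suitably across the cells.

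**4. Is the arm comparison given elsewhere?** The Data Analyses paragraph does not mention arm, intervention, supplementation, visit or change from baseline. Its exposures are biomarker levels, and its groupings are APO status, race and parity. The statistical text under Aim 2 covers survey scores, pill-count adherence and interviews only. Section D's remark on effect sizes has no estimator attached.

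**5. How precise would the missing comparison be?** The plan's completer figure reproduces: 56 x (1 - 0.25) = 42, or 21 per arm. In SD units, with n per arm:

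- Unadjusted half-width = t(0.975, 2n-2) x sqrt(2/n). For n = 21: 2.021 x 0.309 = 0.62. For n = 28: 2.005 x 0.267 = 0.54.
- Adjusted for Visit 1 value and race = t(0.975, 2n-4) x sqrt(2/n) x sqrt(1 - r²), where r is the Visit 1 to Visit 2 correlation. The document gives no r, so a range is assumed.

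| n per arm | Unadjusted | r = 0.3 | r = 0.5 | r = 0.7 |
|---|---|---|---|---|
| 21 | 0.62 | 0.60 | 0.54 | 0.45 |
| 28 | 0.54 | 0.51 | 0.46 | 0.38 |

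An arm x race interaction at 21 per arm has an unadjusted half-width of about 1.2 SD (50:50 race split) to 1.4 SD (28:72), so it can only be exploratory.

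**The case against.** The strongest reply is that the intent is plain. Section B proposes to test responses to the supplement in 28 intervention and 28 control women, and section D gives the arms, the two visits and an assumed Cohen's d of about 0.50. A reader can infer the between-arm contrast. That is fair as to intent, and the plan can still be amended before analysis. But no passage supplies a model, a visit, a way of handling baseline or an effect measure, and the analysis that is written answers a different question.

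A second reply is that APO status may mean APO type. Section E.1 speaks of vascular APO, and pregnancy history is collected. This reading is possible, but the document never defines the term that way, so the sponsor should be asked.

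Third, the rank calculation only formalises the fact that a constant cannot be compared with itself, and the half-widths describe the proposed analysis rather than an error in the plan. Both points are correct. The conclusion rests on the text, and the figures show what survives and what precision to expect.

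Finally, adding the arm comparison exposes the sample size. At d = 0.50 and an assumed two-sided alpha of 0.05, unadjusted power is about 37% with 21 per arm and 46% with 28 (normal approximation). That is a separate matter and no reason to leave the comparison out.

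**Conclusion.** The concern holds, and the plan must be corrected before analysis. Under the base eligibility criteria the APO-status test, interaction and stratification cannot be estimated: there are no APO-negative women, and 4 of 8 model columns are redundant. With the GDM option, APO status has no stated meaning. By itself this wastes part of the plan and biases nothing.

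The serious consequence is that the only analysis text for Aim 1 contains no comparison of the randomised arms, so the trial's main question and its stated key output have no defined estimate. These conclusions need no numerical assumption. Only the GDM ranks (assumed counts and coding) and the adjusted half-widths (assumed r of 0.3 to 0.7) depend on figures that the document does not give.

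**What to change.** First settle what APO status means. If APO type was intended (for example vascular APO versus GDM), define it and state how women with GDM only are coded. Otherwise delete the APO-status test, interaction and stratification. Then add to the Data Analyses paragraph:

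> For each biomarker and vascular outcome, the Visit 2 value will be compared between randomised arms with a linear model adjusted for the Visit 1 value and race (the randomisation stratum). The between-arm difference will be reported with a 95% CI. Arm x race will be an exploratory interaction.

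State in advance which biomarkers will be log-transformed, so that this is not decided from the observed distributions. In the same edit, name the primary outcome, the analysis set and the handling of missing Visit 2 values, since 56 women are expected to fall to 42. Keep the biomarker-outcome regressions as secondary analyses.

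Other valid between-arm models exist. The essential step is to fix one now. The cost is analysis wording only: arm, race and both visits' values are already to be collected, and no new visits or participants are needed for this change. The sample-size statement should be reviewed separately against the comparison once it is written down.
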